If a new lesion is equivocal, for example because of its small size, continued therapy and follow-up evaluation will clarify if it represents truly new disease. If repeat scans confirm there is definitely a new lesion, then progression should be declared using the date of the initial scan.

EVALUATION OF BEST OVERALL RESPONSE

The best overall response is the best response recorded from the start of the study treatment until the end of treatment taking into account any requirement for confirmation. The patient's best overall response assignment will depend on the findings of both target and non-target disease and will also take into consideration the appearance of new lesions.

Time point response

It is assumed that at each protocol specified time point, a response assessment occurs. **Table A-1** on the next page provides a summary of the overall response status calculation at each time point for patients who have measurable disease at baseline.

Missing assessments and unevaluable designation

When no imaging/measurement is done at all at a particular time point, the patient is not evaluable (NE) at that time point. If only a subset of lesion measurements is made at an assessment, usually the case is also considered NE at that time point, unless a convincing argument can be made that the contribution of the individual missing lesion(s) would not change the assigned time point response. This would be most likely to happen in the case of PD. For example, if a patient had a baseline sum of 50 mm with three measured lesions and at follow-up only two lesions were assessed, but those gave a sum of 80 mm, the patient will have achieved PD status, regardless of the contribution of the missing lesion.

Best overall response: all time points

The *best overall response* is determined once all the data for the patient is known.

Table A-1 **Time point response: patients with target (+/- non-target) disease**

Target lesions	Non-target lesions	New lesions	Overall response
CR	CR	No	CR
CR	Non-CR/non-PD	No	PR
CR	Not evaluated	No	PR
PR	Non-PD or not all evaluated	No	PR
SD	Non-PD or not all evaluated	No	SD
Not all evaluated	Non-PD	No	NE
PD	Any	Yes or No	PD
Any	PD	Yes or No	PD
Any	Any	Yes	PD

CR = complete response, PR = partial response, SD = stable disease, PD = progressive disease, and NE = inevaluable.

Best response determination in trials where confirmation of complete or partial response IS required: Complete or partial responses may be claimed only if the objective response is confirmed on a follow-up scan obtained no less than 4 weeks after the initial scan demonstrating an objective response. In this circumstance, the best overall response can be interpreted as in **Table A-2**.

Table A-2 Best overall response when confirmation of CR and PR required

Overall response First time point	Overall response Subsequent time point	BEST overall response
CR	CR	CR
CR	PR	SD, PD or PR ^a
CR	SD	SD
CR	PD	SD
CR	NE	SD
PR	CR	PR
PR	PR	PR
PR	SD	SD
PR	PD	SD provided minimum criteria for SD duration met, otherwise, PD
PR	NE	SD provided minimum criteria for SD duration met, otherwise, NE
NE	NE	NE

CR = complete response, PR = partial response, SD = stable disease, PD = progressive disease, and NE = inevaluable.

a If a CR is *truly* met at first time point, then any disease seen at a subsequent time point, even disease meeting PR criteria relative to baseline, makes the disease PD at that point (since disease must have reappeared after CR). Best response would depend on whether minimum duration for SD was met. However, sometimes 'CR' may be claimed when subsequent scans suggest small lesions were likely still present and in fact the patient had PR, not CR at the first time point. Under these circumstances, the original CR should be changed to PR and the best response is PR.

Special notes on response assessment

When nodal disease is included in the sum of target lesions and the nodes decrease to 'normal' size (<10 mm), they may still have a measurement reported on scans. This measurement should be recorded even though the nodes are normal in order not to overstate progression should it be based on increase in size of the nodes. As noted earlier, this means that patients with CR may not have a total sum of 'zero' on the case report form (CRF).

Patients with a global deterioration of health status requiring discontinuation of treatment without objective evidence of disease progression at that time should be reported as 'symptomatic deterioration'. Every effort should be made to document objective progression even after discontinuation of treatment. Symptomatic deterioration is *not* a descriptor of an objective response: it is a reason for stopping study therapy. The objective response status of such patients is to be determined by evaluation of target and non-target disease as shown in **Table A-1** and **Table A-2**.

For equivocal findings of progression (e.g., very small and uncertain new lesions; cystic changes or necrosis in existing lesions), treatment may continue until the next scheduled

assessment. If at the next scheduled assessment, progression is confirmed, the date of progression should be the earlier date when progression was suspected.

CONFIRMATION/DURATION OF RESPONSE

Confirmation

Objective responses should be confirmed by CT and/or MRI scans obtained no less than 4 weeks after the original scan.

Duration of overall response

The duration of overall response is measured from the time measurement criteria are first met for CR/PR (whichever is first recorded) until the first date that recurrent or progressive disease is objectively documented (taking as reference for progressive disease the smallest measurements recorded on study). The duration of overall complete response is measured from the time measurement criteria are first met for CR until the first date that recurrent disease is objectively documented.

Duration of stable disease

Stable disease is measured from the start of the treatment until the criteria for progression are met, taking as reference the *smallest sum on study* (if the baseline sum is the smallest, this is the reference for calculation of PD).

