6.8 Concomitant Therapy

MGA271, pembrolizumab, and MGA012 are the only cancer drugs to be administered routinely in this study. No concomitant anti-cancer therapy will be given.

All concomitant medications and blood products administered during the patient's participation in the study until the post treatment follow-up visit must be recorded in the source document and on the electronic Case Report Form (eCRF). All changes in infusions, including interruptions and their duration as well as reductions in rate and duration must be recorded.

The following rules concerning concurrent treatment(s) will apply in this study:

- Any other anti-neoplastic therapies including but not limited to chemotherapy or other small molecules, biologics, or radiotherapy are not allowed. For patients who require palliative radiotherapy (i.e., cumulative dose less than 3000 rads, limited field of distribution) for reasons other than disease progression, therapy with MGA271 and pembrolizumab may be interrupted for up to 4 weeks. Palliative radiotherapy may not be given concurrently with either MGA271 or pembrolizumab or MGA012. Treatment with palliative therapy should be initiated at least 24 hours after receiving either MGA271 or pembrolizumab or MGA012, and re-initiation of MGA271 or pembrolizumab or MGA012 can begin one day after the completion of palliative radiotherapy if there were no complications associated with the radiotherapy. Palliative radiotherapy fields also should not overlap tumor lesions that have previously been designated as target lesions. In the event that this is medically necessary for palliative purposes, the patient may continue on study, but will no longer be evaluable for objective response from the time palliative radiotherapy is initiated.
- Patients may not receive other investigational drugs during the period of study participation.
- Because MGA271, pembrolizumab, and MGA012 have a mechanism of action dependent upon the engagement of T lymphocytes, the use of corticosteroids should be limited to the extent possible. Chronic doses of corticosteroids in excess of 10 mg daily of prednisone or equivalent is prohibited other than for the management of drug-related adverse experiences. Steroids may be employed in the treatment of suspected MGA271- or pembrolizumab- or MGA012-associated immune-inflammatory or autoimmune AEs in consultation with the Sponsor.

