7.11 Efficacy and/or Pharmacokinetic and Pharmacodynamic Assessments

7.11.1 Efficacy Assessments

7.11.1.1 Treatment of Patients According to Principles of Immune-Related Response Criteria

Tumor assessments will be obtained at screening using CT and/or MRI scans at time intervals as specified in the [Appendix 1](#) (Time and Events Table). The study is divided into 6 Tumor Assessment Cycles; the first is a 6-week cycle called the Initial Tumor Assessment Cycle and Cycles 2 through 6 are 9-week cycles. The tumor assessment takes place at the end of each cycle. Treatment will continue until patients have completed study therapy and required follow-up, experienced disease progression, or have been withdrawn from the study (see [Section 4.4](#) and [Section 5.3](#)). At each on-treatment tumor assessment time point, the objective response status will be determined. In the context of the statistical analysis for this trial, objective response determination and the assessment of best overall response (BOR) will be defined using both conventional RECIST1.1 criteria ([Appendix 5](#)) as well as an adaptation of these criteria, designated as immune-related response criteria (irRC) (i.e., irRECIST as defined in [Appendix 6](#)). Patient management decisions, however, will be made solely based on the immune-related response criteria ([Appendix 6](#)).

For patients who demonstrate acceptable tolerability of treatment with MGA271, and an objective response assessment of irCR, irPR or irSD, or unconfirmed clinically-stable irPD, therapy may be continued (see [Section 4.4](#) and [Section 5.3](#)).

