For patients who are otherwise clinically stable, but have met conventional criteria for PD, therapy may be continued at the discretion of the investigator pending confirmation of progression at the next scheduled tumor assessment. This approach allows for limited treatment of patients beyond the initial radiographic documentation of disease progression, assuming that patients are tolerating therapy adequately, that patients remain otherwise clinically stable despite this initial radiographic evidence of disease progression and that the Investigator feels the patient may still derive benefit from continuation of therapy. Treatment of patients according to irRC (i.e., irRECIST) principles is supported by well-documented evidence that in some patients treated with T cell directed, immune-modulatory agents, their tumors can evolve to an objective response after an initial period characterized by either apparent radiographic growth of target lesions or the development of new target lesions that would otherwise meet the criteria for disease progression using conventional response criteria ([67](#))

For patients in whom progression is confirmed at the next scheduled tumor assessment, the criteria for immune-related PD (irPD) will have been met, and treatment with MGA271, pembrolizumab, or MGA012 should be discontinued. The patient should be removed from study participation after completion of protocol specified follow-up (see [Section 8.3](#) and [Appendix 1](#)). For patients who experience an objective response of immune-related complete response (irCR) or immune-related partial response (irPR), responses will be considered unconfirmed until the response has been documented by a subsequent confirmatory scan obtained no less than 4 weeks after the initial scan demonstrating an objective response.

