All other lesions (or sites of disease) including pathological lymph nodes should be identified as *non-target lesions* and should also be recorded at baseline. Measurements are not required and these lesions should be followed as 'present', 'absent', or in rare cases 'unequivocal progression. In addition, it is possible to record multiple non-target lesions involving the same organ as a single item on the case record form (e.g. 'multiple enlarged pelvic lymph nodes' or 'multiple liver metastases').

RESPONSE CRITERIA

This section provides the definitions of the criteria used to determine objective tumor response for target lesions.

Evaluation of target lesions

Complete Response (CR): Disappearance of all target lesions. Any pathological lymph nodes (whether target or non-target) must have reduction in short axis to < 10 mm.

Partial Response (PR): at least a 30% decrease in the sum of diameters of target lesions, taking as reference the baseline sum diameters.

Progressive Disease (PD): at least a 20% increase in the sum of diameters of target lesions, taking as reference the *smallest sum on study* (this includes the baseline sum if that is the smallest on study). In addition to the relative increase of 20%, the sum must also demonstrate an absolute increase of at least 5 mm. (*Note*: the appearance of one or more new lesions is also considered progression).

Stable Disease (SD): Neither sufficient shrinkage to qualify for PR nor sufficient increase to qualify for PD, taking as reference the smallest sum diameters while on study.

Special notes on the assessment of target lesions

Lymph nodes. Lymph nodes identified as target lesions should always have the actual short axis measurement recorded (measured in the same anatomical plane as the baseline examination), even if the nodes regress to below 10 mm on study. This means that when lymph nodes are included as target lesions, the ‘sum’ of lesions may not be zero even if complete response criteria are met, since a normal lymph node is defined as having a short axis of <10 mm. In order to qualify for CR, each node must achieve a short axis <10 mm. For PR, SD and PD, the actual short axis measurement of the nodes is to be included in the sum of target lesions.

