6.6.2 Tumor Size Change from Baseline

The tumor size percent change from baseline over time will be summarized and presented by spider plot. The best tumor size percent change from baseline prior to the date of first PD or initiation of new anticancer therapy will be presented by waterfall plot. Patients with CR or PR at time of last assessment will be censored at the time of their last tumor assessment. Using statistical notation, if y_t denotes the sum of the measurements at some post-baseline timepoint and y_0 denotes the sum of the measurements at baseline, the percent change from baseline will be calculated as:

$$(y_t - y_0) / y_0 \times 100$$

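### Conventional RECIST best response runs to the end of treatment with no readable stop at first RECIST PD, so a partial response after target-lesion progression can count in the RECIST ORR

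*Protocol*

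**What the plan says.** Appendix 5 (Evaluation of Best Overall Response) takes conventional RECIST best response as "the best response recorded from the start of the study treatment until the end of treatment", subject to confirmation, and adds that it "is determined once all the data for the patient is known". PR at a time point is "at least a 30% decrease in the sum of diameters of target lesions, taking as reference the baseline sum diameters". PD is judged against the smallest sum on study. Table A-2, which gives best response when confirmation is required, has no row for PD followed by CR or PR.

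On management, Protocol 7.11.1.1 states: "Patient management decisions, however, will be made solely based on the immune-related response criteria". It provides that, where clinically stable patients "have met conventional criteria for PD, therapy may be continued at the discretion of the investigator pending confirmation of progression", treatment runs on to the next scheduled scan. The reason given is that in some patients "their tumors can evolve to an objective response after an initial period characterized by" apparent growth or new lesions.

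Protocol 9.5 and SAP 5.1 define ORR as CR or PR, confirmed at least 28 days later, among response evaluable patients. The readable part of SAP 6.6.1 says the same. None of them mentions a cut-off at first PD. SAP 6.6.2 does use one for a different output: best percent change in tumor size "prior to the date of first PD or initiation of new anticancer therapy will be presented by waterfall plot".

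**The concern.** A secondary objective is to describe activity by RECIST 1.1 and by irRECIST. The two are worth reporting side by side only if RECIST treats first progression as final and irRECIST allows for later response. Here a RECIST PD does not end treatment, and the RECIST response window closes only when treatment does. The patients whom the protocol treats past progression, in the expectation that some will respond late, can therefore enter the RECIST numerator too.

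The results at stake are the expansion-cohort ORRs, which come from cohorts of at most 16 or 20 patients. Protocol 2.3.1.1.2 already compares ORRs from this study with published anti-PD-1 monotherapy results. A RECIST ORR that includes responses after progression is not like for like with one that stops at first PD. The same patient would also have a RECIST PFS event that precedes the RECIST response.

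**Working it through.** **The plan's own figures.** Expansion total: 16 + 16 + 4 × 20 = 112, as stated. Interim ORRs in Protocol Table 1: 33.3% of 18 corresponds to 6/18, and 35.7% of 14 to 5/14.

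**A patient path under Appendix 5.** Scans fall on Day 42, then at the end of each 9-week cycle: 42 + 63 = 105 and 105 + 63 = 168. Take a hypothetical baseline sum of 100 mm, no new lesions and no non-target progression, with treatment continuing throughout.

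| Day | Sum (mm) | Against smallest earlier sum | Against baseline | RECIST status |
|---|---|---|---|---|
| 42 | 125 | (125 − 100)/100 = +25%, +25 mm | +25% | PD |
| 105 | 65 | (65 − 100)/100 = −35% | −35% | PR |
| 168 | 62 | (62 − 65)/65 = −4.6% | −38% | PR, confirmed 63 days later |

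The Day 42 increase passes both PD thresholds (20% and 5 mm). The confirmation interval, 168 − 105 = 63 days, exceeds 28. The Day 42 progression is not confirmed at Day 105, so 7.11.1.1 allows treatment to go on.

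**What each analysis does with this patient.**
- RECIST best response, by the general definition: PR, so the patient counts in the RECIST ORR. With a cut-off at first PD it is PD.
- RECIST PFS (SAP 5.1 and Table 3): event at Day 42, which is 63 days before the first PR.
- Duration of response (SAP 6.6.3: end date minus response date plus 1, divided by 365.25/12). If the end date is the first PD: 42 − 105 + 1 = −62 days, and −62/30.4375 = −2.0 months. If it is a later PD, death or the last scan, the value is positive. The SAP does not say which PD date applies.
- Waterfall plot (SAP 6.6.2): the −35% and −38% values fall after first PD and are left out.

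**New lesions.** Table A-1 gives overall PD at any time point where a new lesion is recorded, whatever the target lesions do. A patient whose PD came from a new lesion that persists stays at PD. The route is therefore mainly target-lesion growth.

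**Size per patient (1/n).** 1/20 = 5.0 points; 1/16 = 6.25, or 6.3; 1/14 = 7.1.

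**Illustration on the interim figures.** The documents give no count of responders after progression. Assume 0, 1 or 2 per cohort. Intervals are two-sided 95% exact binomial, the SAP's method.

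| Reclassified | SCCHN, N=18 | NSCLC, N=14 |
|---|---|---|
| 0 | 6/18 = 33.3% (13.3 to 59.0) | 5/14 = 35.7% (12.8 to 64.9) |
| 1 | 5/18 = 27.8% (9.7 to 53.5) | 4/14 = 28.6% (8.4 to 58.1) |
| 2 | 4/18 = 22.2% (6.4 to 47.6) | 3/14 = 21.4% (4.7 to 50.8) |

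**The case against.** The strongest reply is that no rule expressly counts such a patient as a responder. Table A-2 is silent on PD followed by PR, so the result rests on the general definition. SAP 6.6.1 is redacted around the ORR rule, and programming specifications sit in a separate plan, so a cut-off may exist out of sight. Both points stand as limits. They do not remove the concern: the general definition is explicit about its window, and the unredacted definitions in Appendix 5, Protocol 9.5 and SAP 5.1 have no stop.

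It is also fair to say that the study is descriptive, that ORR is a secondary and preliminary measure, and that a one-patient shift is small beside intervals as wide as 13.3% to 59.0%. That limits the weight of the point, but a definitional shift is systematic and upward, and the interval does not reflect it.

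A reader might infer more than the documents support:
- **That responses after a new anticancer therapy would count.** Protocol 6.8 bars other anti-neoplastic treatment on study and the window ends with treatment, so this is largely covered.
- **That radiotherapy to target lesions is unhandled.** Protocol 6.8 says such a patient "will no longer be evaluable for objective response from the time palliative radiotherapy is initiated". The readable SAP does not repeat this, but that is not a contradiction.
- **That RECIST and irRECIST become the same.** New lesions still separate them: PD under Appendix 5, added to the tumor sum under Appendix 6.
- **That duration of response cannot be computed.** It can, once a PD date is chosen. The fault is that the choice is not stated.
- **That the ORR table and waterfall plot ought to agree.** They measure different things and can differ for other reasons, such as confirmation.

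**Conclusion.** The point holds in this form: as readable, the plan lets a confirmed PR after target-lesion progression count in the conventional RECIST ORR, after that patient's RECIST PFS event, and leaves the end date for duration of response unstated. Each such patient moves ORR by 5.0 to 7.1 points for n from 20 down to 14.

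This assumes that Appendix 5 governs the derivation, that the redacted part of SAP 6.6.1 and the programming plan contain no cut-off, and that at least one patient follows the path. The number may be zero; the protocol says only that some patients respond this way and gives no rate. The interim ORRs cannot be called inflated: Protocol 2.3.1.1.2 does not say which criteria they use or whether any responder had progressed first. The primary safety objective is not affected. The gap should be closed before analysis, because the design makes the sequence foreseeable.

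**What to change.** Add to SAP 5.1 and 6.6.1: RECIST 1.1 best overall response and ORR use assessments up to and including first RECIST PD (the progression date used for RECIST PFS) and before any new anticancer therapy; responses first seen later are reported under irRECIST only. This brings ORR into line with the cut-off events already used in SAP 6.6.2. It also settles duration of response, since no RECIST response could then begin after RECIST PD. If the redacted text or the programming plan already contains this rule, it need only be repeated in SAP 5.1.

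The cost is one sentence. No new data are needed and patient management does not change. The downside is that the RECIST ORR may be slightly less favourable; late responses would still be reported under irRECIST.

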Appendix 6 Immune-Related RECIST Guidelines

(Adapted from Wolchok 2009 (67))

All patients will be required to have at least 1 measurable lesion to be considered as having measurable disease at baseline for the determination of eligibility for this study. Measurable lesions are defined below.

MEASURABILITY OF TUMOR AT BASELINE

DEFINITIONS

At baseline, tumor lesions/lymph nodes will be categorized measurable or non-measurable as follows:

Measurable

Tumor lesions: Must be accurately measured in at least one dimension (*longest* diameter in the plane of measurement is to be recorded) with a *minimum* size of:

- 10 mm by CT scan (CT scan slice thickness no greater than 5 mm).
- 10 mm caliper measurement by clinical exam (lesions which cannot be accurately measured with calipers should be recorded as non-measurable).
- 20 mm by chest X-ray.

Malignant lymph nodes: To be considered pathologically enlarged and measurable, a lymph node must be ≥ 15 mm in *short* axis when assessed by CT scan (CT scan slice thickness no greater than 5 mm). At baseline and in follow-up, only the *short* axis will be measured and followed. See also notes below on 'Baseline documentation of target and non-target lesions' for information on lymph node measurement.

Non-measurable

All other lesions, including small lesions (longest diameter < 10 mm or pathological lymph nodes with ≥ 10 to < 15 mm short axis) as well as truly non-measurable lesions. Lesions considered truly non-measurable include: leptomeningeal disease, ascites, pleural or pericardial effusion, inflammatory breast disease, lymphangitic involvement of skin or lung, abdominal masses/abdominal organomegaly identified by physical exam that is not measurable by reproducible imaging techniques.

Special considerations regarding lesion measurability

Bone lesions, cystic lesions, and lesions previously treated with local therapy require particular comment:

Bone lesions:

- Bone scan, PET scan or plain films are not considered adequate imaging techniques to measure bone lesions. However, these techniques can be used to confirm the presence or disappearance of bone lesions.
- Lytic bone lesions or mixed lytic-blastic lesions, with identifiable soft tissue components, that can be evaluated by cross sectional imaging techniques such as CT or MRI can be considered as measurable lesions if the soft tissue component meets the definition of measurability described above.
- Blastic bone lesions are non-measurable.

Cystic lesions:

- Lesions that meet the criteria for radiographically defined simple cysts should not be considered as malignant lesions (neither measurable nor non-measurable) since they are, by definition, simple cysts.
- 'Cystic lesions' thought to represent cystic metastases can be considered as measurable lesions, if they meet the definition of measurability described above. However, if non-cystic lesions are present in the same patient, these are preferred for selection as target lesions.

Lesions with prior local treatment:

- Tumor lesions situated in a previously irradiated area, or in an area subjected to other loco-regional therapy, are not considered measurable unless there has been demonstrated progression in the lesion prior to study enrollment.

SPECIFICATIONS BY METHODS OF MEASUREMENTS**Measurement of lesions**

All measurements should be recorded in metric notation, using calipers if clinically assessed. All baseline evaluations should be performed as close as possible to the treatment start and never more than 4 weeks before the beginning of the treatment.

Method of assessment

The same method of assessment and the same technique should be used to characterize each identified and reported lesion at baseline and during follow-up. Imaging based evaluation should always be done rather than clinical examination unless the lesions(s) being followed cannot be imaged but are assessable by clinical exam.

Clinical lesions: Clinical lesions will only be considered measurable when they are superficial and ≥ 10 mm diameter as assessed using calipers (e.g., skin nodules). For the case of skin lesions, documentation by color photography including a ruler to estimate the size of the lesion is suggested. As noted above, when lesions can be evaluated by both clinical exam and imaging, imaging evaluation should be undertaken since it is more objective and may also be reviewed at the end of the study.

Chest X-ray: Chest CT is preferred over chest X-ray, particularly when progression is an important endpoint, since CT is more sensitive than X-ray, particularly in identifying new lesions. However, lesions on chest X-ray may be considered measurable if they are clearly defined and surrounded by aerated lung.

CT, MRI: CT is the best currently available and reproducible method to measure lesions selected for response assessment. This guideline has defined measurability of lesions on CT scan based on the assumption that CT slice thickness is 5 mm or less. When CT scans have slice thickness greater than 5 mm, the minimum size for a measurable lesion should be twice the slice thickness. MRI is also acceptable in certain situations (e.g. for body scans).

Ultrasound: Ultrasound is not useful in assessment of lesion size and should not be used as a method of measurement. Ultrasound examinations cannot be reproduced in their entirety for independent review at a later date and, because they are operator dependent, it cannot be guaranteed that the same technique and measurements will be taken from one assessment to the next. If new lesions are identified by ultrasound in the course of the study, confirmation by CT or MRI is advised. If there is concern about radiation exposure at CT, MRI may be used instead of CT in selected instances.

Endoscopy, laparoscopy: The utilization of these techniques for objective tumor evaluation is not advised.

Tumor markers: Tumor markers will not be used to assess *objective* tumor response.

TUMOR RESPONSE EVALUATION

ASSESSMENT OF OVERALL TUMOR BURDEN AND MEASURABLE DISEASE

To assess objective response or future progression, it is necessary to estimate the *overall tumor burden at baseline* and use this as a comparator for subsequent measurements. Only patients with measurable disease at baseline should be included. Measurable disease is defined by the presence of at least one measurable lesion (as detailed above).

BASELINE DOCUMENTATION OF 'TARGET' AND 'NON-TARGET' LESIONS

Where more than one measurable lesion is present at baseline all lesions up to a maximum of five lesions total (and a maximum of two lesions per organ) representative of all involved

organs should be identified as *target lesions* and will be recorded and measured at baseline. For example, in instances where patients have only one or two organ sites involved, a maximum of two and four lesions respectively will be recorded). Target lesions should be selected on the basis of their size (lesions with the longest diameter), be representative of all involved organs, but in addition should be those that lend themselves to *reproducible repeated measurements*. It may be the case that, on occasion, the largest lesion does not lend itself to reproducible measurement in which circumstance the next largest lesions which can be measured reproducibly should be selected.

Lymph nodes merit special mention since they are normal anatomical structures which may be visible by imaging even if not involved by tumor. As noted previously, pathological nodes which are defined as measurable and may be identified as target lesions must meet criterion of a short axis of ≥ 15 mm by CT scan. Only the *short axis* of these nodes will contribute to the baseline sum. The short axis of the node is the diameter normally used by radiologists to judge if a node is involved by solid tumor. Nodal size is normally reported as two dimensions in the plane in which the image is obtained (for CT scan this is almost always the axial plane; for MRI the plane of acquisition may be axial, sagittal or coronal). The smaller of these measures is the short axis. For example, an abdominal node which is reported as being 20 mm x 30 mm has a short axis of 20 mm and qualifies as a malignant, measurable node. In this example, 20 mm should be recorded as the node measurement. All other pathological nodes (those with short axis ≥ 10 mm but < 15 mm) should be considered non-target lesions. Nodes that have a short axis < 10 mm are considered non-pathological and should not be recorded or followed.

A *sum of the diameters* (longest for non-nodal lesions, short axis for nodal lesions) for all target lesions will be calculated and reported as the *baseline sum diameters*. If lymph nodes are to be included in the sum, then as noted above, only the *short axis* is added into the sum. The baseline sum diameters will be used as reference to further characterize any objective tumor regression in the measurable dimension of the disease.

All other lesions (or sites of disease) including pathological lymph nodes should be identified as *non-target lesions* and should also be recorded at baseline. Measurements are not required and these lesions should be followed as ‘present’, ‘absent’, or in rare cases ‘unequivocal progression’. In addition, it is possible to record multiple non-target lesions involving the same organ as a single item on the case record form (e.g., ‘multiple enlarged pelvic lymph nodes’ or ‘multiple liver metastases’).

RESPONSE CRITERIA

This section provides the definitions of the criteria used to determine objective tumor response for target lesions by immune-related response criteria (i.e., irRECIST).

Evaluation of target lesions

Immune-Related Complete Response (irCR): Disappearance of all target lesions. Any pathological lymph nodes (whether target or non-target) must have reduction in short axis to < 10 mm.

Immune-Related Partial Response (irPR): at least a 30% decrease in the sum of diameters of target lesions, taking as reference the baseline sum diameters.

Immune-related Progressive Disease (irPD): at least a 20% increase in the sum of diameters of target lesions, taking as reference the *smallest sum on study* (this includes the baseline sum if that is the smallest on study). In addition to the relative increase of 20%, the sum must also demonstrate an absolute increase of at least 5 mm.

Unlike conventional RECIST criteria, the appearance of new measurable lesions does not automatically denote disease progression under immune-related response criteria. Rather the dimensions of new measurable lesions are added to overall sum of tumor diameters for determination of objective response status. Patients will not be considered as having progression unless the new overall sum of diameters has increased by $\geq 20\%$ from the smallest sum of tumor diameters achieved while on study.

Immune-Related Stable Disease (irSD): Neither sufficient shrinkage to qualify for PR nor sufficient increase to qualify for PD, taking as reference the smallest sum diameters while on study.

Special notes on the assessment of target lesions

Lymph nodes. Lymph nodes identified as target lesions should always have the actual short axis measurement recorded (measured in the same anatomical plane as the baseline examination), even if the nodes regress to below 10 mm on study. This means that when lymph nodes are included as target lesions, the ‘sum’ of lesions may not be zero even if complete response criteria are met, since a normal lymph node is defined as having a short axis of <10 mm. In order to qualify for irCR, each node must achieve a short axis <10 mm. For irPR, irSD and irPD, the actual short axis measurement of the nodes is to be included in the sum of target lesions.

Target lesions that become ‘too small to measure’. While on study, all lesions (nodal and non-nodal) recorded at baseline should have their actual measurements recorded at each subsequent evaluation, even when very small (e.g., 2 mm). However, sometimes lesions or lymph nodes which are recorded as target lesions at baseline become so faint on CT scan that the radiologist may not feel comfortable assigning an exact measure and may report them as being ‘too small to measure’. When this occurs it is important that a value be recorded on the case report form. If it is the opinion of the radiologist that the lesion has likely disappeared, the measurement should be recorded as 0 mm. If the lesion is believed to be present and is faintly seen but too small to measure, a default value of 5 mm should be assigned (*Note*: It is less likely that this rule will be used for lymph nodes since they usually have a definable size when normal and are frequently surrounded by fat such as in the retroperitoneum; however, if a lymph node is believed to be present and is faintly seen but too small to measure, a default value of 5 mm should be assigned in this circumstance as well). This default value is derived from the 5 mm CT slice thickness (but should not be changed with varying CT slice thickness). The measurement of these lesions is potentially non-reproducible, therefore providing this default value will prevent false responses or progressions based upon

measurement error. However, if the radiologist is able to provide an actual measure, that should be recorded, even if it is below 5 mm.

Lesions that split or coalesce on treatment. When non-nodal lesions ‘fragment’, the longest diameters of the fragmented portions should be added together to calculate the target lesion sum. Similarly, as lesions coalesce, a plane between them may be maintained that would aid in obtaining maximal diameter measurements of each individual lesions. If the lesions have truly coalesced such that they are no longer separable, the vector of the longest diameter in this instance should be the maximal longest diameter for the ‘coalesced lesion’.

Evaluation of non-target lesions

This section provides the definitions of the criteria used to determine the tumor response for the group of non-target lesions. While some non-target lesions may actually be measurable, they need not be measured and instead should be assessed only *qualitatively* at the time points specified in the protocol.

Immune-Related Complete Response (irCR): Disappearance of all non-target lesions. All lymph nodes must be non-pathological in size (<10mm short axis).

Non-CR/Non-PD: Persistence of one or more non-target lesions(s)

Immune-Related Progressive Disease (irPD): Unlike conventional RECIST 1.1, new measurable lesions or increases in the size of non-target lesions do not define PD in isolation in the immune-related response criteria. Rather, immune-related PD is established if the sum of diameters is $\geq 20\%$ of the nadir of the sum of diameters for a given patient.

New Lesions

The appearance of new malignant lesions alone does not denote disease progression. Instead, the diameter of new lesions is added to the sum of diameters for target and non-target lesions.

EVALUATION OF BEST OVERALL RESPONSE

The best overall response is the best response recorded from the start of the study treatment until the end of treatment taking into account any requirement for confirmation. The patient’s best overall response assignment will depend on the findings of both target and non-target disease.

Time point response

It is assumed that at each protocol specified timepoint, a response assessment occurs. For patients experiencing irCR or irPR, a confirmatory scan obtained no less than 4 weeks after the original scan is required to confirm the objective response. For patients experiencing irPD, but who demonstrate acceptable tolerability of treatment as evaluated by the Investigator, a confirmatory scan obtained no less than 4 weeks after the original scan is required for the confirmation of irPD.

